1.0 Background

Many children who are deaf and hard of hearing (DHH) are not achieving the language skills of their peers with typical hearing despite access to audiological, educational, and speech-language intervention (Antia et al., 2020; Boons et al., 2013; Geers et al., 2017; Geers & Sedey, 2011; Kyle & Harris, 2011; Lund, 2016; Nittrouer et al., 2019; Qi & Mitchell, 2012; Ruben, 2018; Werfel, 2017). Our **long-term goal is to increase the effectiveness and efficiency of language learning for children who are DHH through individualized interventions**, thereby improving their long-term educational and vocational success. Despite persistent deficits in language skills compared with hearing peers and the obligation to provide evidence-based services, few experimental language intervention studies for children who are DHH have been conducted (Brennan-Jones et al., 2014; Kaipa & Danser, 2016; Luckner & Cooke, 2010; Roberts, 2019). This paucity of evidence hampers practitioners' implementation of individualized, evidence-based interventions. As a result, students are at risk for receiving ineffective or even detrimental interventions.

Identifying active ingredients of language interventions for children who are DHH would build our theoretical understanding about what facilitates and impedes their language development. Once identified, active ingredients can be enhanced (e.g., modify intensity) through empirical investigations that consider individual differences. For children who are DHH, **retrieval practice** (testing effect) presents as a potential active ingredient for language intervention. Retrieving previously presented information (e.g., answering questions or free recall) is **hypothesized to enhance encoding and retention** because it entails the desirable level of effort (desirable difficulties hypothesis; Bjork & Bjork, 2011; Bjork, 1994), builds semantic elaborations and associations between words (elaborative retrieval account; Carpenter, 2009; Carpenter & Yeung, 2017), and/or updates representations to reflect multiple contexts (episodic context account; Karpicke et al., 2014). Replicated findings in children and adults with typical development (Fritz et al., 2007; Goossens et al., 2014; Jones et al., 2016; Karpicke et al., 2014, 2016; Lipowski et al., 2014; Marsh et al., 2012) and emerging results for individuals with disabilities (Coyne et al., 2015; Haebig et al., 2019; Knouse et al., 2016; Leonard, Deevy, et al., 2019; Leonard, Karpicke, et al., 2019; McGregor et al., 2017) have showed positive effects of retrieval practice for academically relevant tasks (e.g., word learning, textbook content, and recalling word lists or pairs) over short retention periods (e.g., one session or one week). For children who are DHH, the few experimental studies on language intervention have often used retrieval practice to some degree, though typically without isolating retrieval practice's effect and under another name (e.g., choral responses, cloze procedures, and receptive and expressive practice; Bobzien et al., 2015; Lund & Douglas, 2016; McDaniel et al., 2019; McDaniel et al., 2018; Reimer, 2019).

Antia, S. D., Lederberg, A. R., Easterbrooks, S., Schick, B., Branum-Martin, L., Connor, C. M., & Webb, M.-Y. (2020). Language and reading progress of young deaf and hard-of-hearing children. *Journal of Deaf Studies and Deaf Education* [advanced online release].

2.0 Rationale and Specific Aims

This study is designed to test the effectiveness and efficiency of retrieval practice for word learning for children who are DHH.

Aim 1: Evaluate the effectiveness and efficiency of retrieval practice with and without feedback for the acquisition and retention for learning novel words. Both conditions are hypothesized to be effective with the feedback condition (i.e., explicit responses about accuracy given to child during teaching sessions) being more efficient than no feedback. Feedback is predicted to improve efficiency because it focuses the child's attention on unmastered material, prevents the illusion of success, and reduces repeated error.

Aim 2: Evaluate the effectiveness and efficiency of retrieval practice with spaced versus massed trials for the acquisition and retention for learning novel words. Both conditions are hypothesized to be effective with spaced trials (i.e., words are interspersed with one another) yielding more efficient learning than massed trials because spaced trials require more effort with fewer cues provided.

3.0 Inclusion/Exclusion Criteria

Children aged 5 to 9 years old who are DHH and use spoken English. Participants must have nonverbal cognitive abilities at least within the average range and receptive and expressive vocabulary standard scores of at least 70 to increase the likelihood that participants will exhibit word learning with a timeframe necessary for the study. Participants must use English as their only spoken language. The word sets must be carefully balanced by certain phonological features. When children are exposed to more than one spoken language, variation in their phonological systems can alter the balancing.

4.0 Enrollment/Randomization

Participants are enrolled via consent from a parent or legal guardian.

Each participant receives two active conditions and the no-teaching control condition. The specific active interventions are determined based on a random number generator.

This study is a clinical trial. Registration on ClinicalTrials.gov completed August 22, 2022.

5.0 Study Procedures

Eligibility Assessments

The assessment battery includes measures of vocabulary (Expressive Vocabulary Test, Third Edition; Peabody Picture Vocabulary Test, Fifth Edition; Dunn, 2018; Williams, 2018), and nonverbal cognition (Leiter International Performance Scale, Third Edition; Roid et al., 2013) skills. Participants must achieve standard scores of at least 70 for spoken receptive and expressive vocabulary skills to increase the likelihood that participants will exhibit word learning within a time frame necessary for the study. Individuals are excluded for below average nonverbal cognitive ability (i.e., standard score below 85 on the Leiter International Performance Scale; Roid et al., 2013). Medical, audiological, and school records supplement caregiver report (e.g., hearing and vision levels). Participants may not have uncorrected vision impairment (i.e., identified vision loss without use of corrective lenses that interferes with eligibility evaluation tasks), or evidence of severe motor impairment (i.e., insufficient motor skills to complete eligibility evaluation tasks independently). Such individuals are unlikely to benefit from the intervention and/or be able to participate in the study tasks.

Descriptive Assessments

Potential participants complete an eligibility evaluation. The assessment battery includes measures of language (Test of Language Development, Intermediate, Fifth Edition; Test of Language Development – Primary, Fifth Edition; Hammill & Newcomer, 2019; Newcomer & Hammill, 2019), speech production (Arizona Articulation Proficiency Scale, Fourth Edition, Fudala & Stegall, 2017), and speech perception (Test of Auditory Processing Skills; Bergeson & Pisoni, 2004; Martin & Brownell, 2005) skills. Caregivers provide demographic and background information and complete the Language Access Profile Tool (Hall & de Anda, 2021) to capture the diverse, dynamic nature of early language access of DHH children. Individual differences in these characteristics may influence word learning efficiency, but specifically how they do is not yet well understood (Carpenter et al., 2016; Jaeger et al., 2015; Karpicke et al., 2016; Moreira et al., 2019). These characteristics are expected to impact the study's external validity and to guide future research.

Procedures for Word Learning Sessions

Novel Word Set Development

Because the AATD requires sets of equal difficulty, the word sets are made of novel words balanced for number of phonemes and syllables, phonotactic probability, and lexical neighborhood density (Storkel, 2003; Storkel & Hoover, 2010a, 2010b). Novel words nearly eliminate the possibility of prior exposure and enable the creation of balanced word sets. Early developing consonants and tense vowels expected to be in the participants' phonemic repertoires (assessed prior to baseline) are primarily used, which aids acquisition receptively and expressively (Leonard et al., 1982). Words do not contain high frequency phonemes (based on acoustic frequency) because they influence word learning and are more likely to be less audible, inaudible, or distorted than lower frequency phonemes for DHH children (Niskar et al., 1998; Shargorodsky et al., 2010; Stelmachowicz et al., 2004b). The following words sets are used: (1) /zod/, /wam/, /getʃ/, and /pib/; (2) /pem/, /vad/, /jotʃ/, and /kub/; (3) /jum/, /tetʃ/, /vob/, and /ked/.

Unfamiliar Objects

Each novel word is randomly paired to an unfamiliar object (e.g., building sets and hardware store items). Testing prior to baseline ensures that participants do not have a consistent form associated with any unfamiliar object or a meaning associated with any of the novel words.

Semantic Content

During intervention the examiner labels the novel object's location (e.g., toy box or bathtub) to increase semantic content. Including this content provides an early step towards using retrieval practice to teach rich vocabulary content that is necessary for achieving age expected language skills without threatening the study's internal validity. Locations are randomly assigned to avoid objects' perceptual features being associated with locations and pretested to ensure participants have the conceptual knowledge of each location to maintain balanced word sets across conditions.

Procedures

All sessions are in-person and videorecorded. Participants must pass a listening check to proceed with the session. Sessions take place in a quiet room (ambient noise ≤ 40 dB as measured by a sound level mobile application) in the child's home, educational setting, or clinic, depending on caregiver preference. Flexibility in location to match caregiver preferences is one way we guard against attrition. Having the examiner for all assessments and intervention sessions be a research team member, rather than school personnel, and conducting the intervention for a relatively short period of time are also designed to guard against attrition.

Dependent Variable Probe

The dependent variable probes (about 10 minutes) test the 12 target words in sets by condition. The primary dependent variable is the percent accuracy (i.e., correct responses / total trials x 100) for labeling target words expressively. The examiner asks the child to label the taught unfamiliar objects and one known object per set (i.e., "What's this?"). The participant is given up to 10 seconds to respond. The secondary dependent variables are the percent accuracy for (a) receptively identifying target words within 5 seconds in a field of six (i.e., four target objects, one foil, and a known object), (b) associated semantic information (i.e., location; "Where's this from?"), and (c) phonological precision for labeling target words expressively. The examiner will not provide any feedback regarding response accuracy for target words during the dependent variable probes. To maintain engagement, the examiner may provide positive reinforcement for non-target behaviors and for identifying the known word for each group, which is expected to be particularly important in the early sessions when accuracy for target words is expected to be low. The study's procedural manual specifies how the examiner should respond to specific child behaviors (e.g., self-corrections and articulatory errors). Primary and secondary coders double enter data into an electronic form using direct systematic observation of the video recordings (Ledford & Gast, 2018).

A research assistant codes at least 25% of sessions in each condition for each participant for interobserver agreement (IOA). The primary coder is blind to which sessions are coded for reliability. All coders are trained to .85 point-by-point agreement for independent coding of three consecutive sessions via recordings of non-participants

(Ledford & Gast, 2018). Training includes reading the coding manual, a didactic presentation, and group coding of non-participants with discrepancy discussions prior to independent coding. Discrepancy discussions occur regularly. If IOA falls below .85 for two sessions, coders must re-train to the initial training criteria.

Baseline Phase

Baseline sessions will occur three times per week and continue until the participant demonstrates a stable pattern of response, with a minimum of three sessions (Ledford & Gast, 2018). Participants complete a listening check then the dependent variable probe to test learning of the 12 target words.

Comparison Phase

Comparison phase sessions occur three times per week after the baseline phase is complete. They begin with a listening check, then the dependent variable probe, and then the two retrieval practice intervention conditions (i.e., feedback-massed, no feedback-massed, feedback-spaced, and no feedback-spaced) for the participant's specific, randomly assigned contrast. In each session, the second condition occurs immediately after the first. Participants are taught the meaning of novel nouns (Lund & Douglas, 2016; Reimer, 2019; Storkel et al., 2019). The independent variable that differentiates the conditions is either the presence of feedback or spaced versus massed trials. All other potentially influential variables are held constant. Table 1 provides a summary of the key teaching procedures for the massed trials conditions (with and without feedback). For the massed trials conditions, all exposures for one word are provided before presenting the next word in an order determined via a random number generator. The spaced trials conditions proceed in the same manner with the exception that the exposures for the four target words are interspersed with one another (e.g., an exposure for word 1, then one for word 3, then one for word 2, etc.). The interspersing of trials across words is especially apparent through the color coding of the steps by word in the Teaching Sessions section of the procedural manual.

Table 1

Summary of Teaching Procedures for Massed Trials Conditions

1. Examiner shows novel object, labels it, and states its location (e.g., "This is a X. The X is from the park.")
2. Examiner and participant color pictures of each novel object to provide shared context
3. Examiner says the label for the novel object ten more times and its location three more times
4. Examiner asks the participant to label the novel object four times and the location twice for retrieval practice

Feedback condition: Examiner provides direct feedback on accuracy and labels the target word (e.g., "Yes, that is a X!" or "Oops, that is a X!")

No-feedback condition: Examiner says statement without target word and then one with it to provide equal exposures to the feedback conditions (e.g., This looks neat. Here's the X!)

5. After the first word, examiner completes same procedure with the three remaining target words in the set
6. Examiner concludes set by asking participant to label and identify the picture for each word and state its location

Feedback condition: Examiner provides direct feedback without naming the target word

No-feedback condition: Examiner does not provide feedback and proceeds to next item

After a participant reaches the criterion of 75% accuracy for expressive labeling for three consecutive sessions for the four target words for one condition, instruction in the remainder of the comparison phase is provided only in the unmastered condition. The comparison phase ends when the unmastered condition reaches criterion. If the participant does not reach mastery after two times the number of sessions to criterion in the mastered condition, the maintenance phase begins then.

Maintenance Phase

Maintenance data are collected weekly via baseline procedures. Maintenance data are first collected a week after the participant achieves mastery for at least one condition. The same dependent variable probe used for the baseline and comparison phases is used to collect maintenance data. Sessions continue for 4 weeks after the comparison phase to permit sufficient time for a trend to emerge for visual analysis. If a consistent pattern is observed before 4 weeks have elapsed, the maintenance phase will end at that time. For example, the maintenance phase ends if a participant exhibits 0% accuracy for all conditions for two consecutive sessions.

Procedural Fidelity

Prior to study sessions, the examiner will demonstrate procedural fidelity (PF) of at least 85% accuracy across three consecutive sessions with non-participants. A research assistant codes at least 25% of study sessions across each phase and condition for each participant. The examiner is blind to which sessions are coded for PF. PF behaviors for probes are consistent across all phases. Only the independent variable varies across the active conditions' PF behaviors. If additional exposures occur, the total number is reported by participant and target word. If PF overall or for providing feedback or

spacing falls below 80% for two sessions, the examiner completes re-training. PF will be analyzed formatively at the behavior level.

6.0 Reporting of Adverse Events or Unanticipated Problems involving Risk to Participants or Others

All adverse events will be reported to the IRB and appropriate regulatory agencies within 7 business days. Any adverse event of a critical nature will be reported within 24 hours.

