8.0 Statistical Considerations

Visual Analysis

Visual analysis is the primary analysis method for single case research design (Ledford & Gast, 2018). Consistent with What Works Clearinghouse practices, we consider five features of the data pattern: level, trend, variability, overlap, and consistency (Kratochwill et al., 2010). We use visual analysis to determine whether there is functional relation between the independent variable (i.e., specific retrieval practice component) and the dependent variable. For each participant with the relevant conditions in their contrast, we examine whether there is evidence of a functional relation between the independent variable and dependent variable. We combine across participants based on the What Works Clearinghouse criteria for strong, moderate, and no evidence of an effect (What Works Clearinghouse, 2016).

Research questions related to effectiveness of the active interventions (i.e., RQs 1-4 and 7-10) will be judged based on accuracy for words taught in the active intervention condition versus those in the no-teaching condition. Research questions related to efficiency (i.e., RQs 5, 6, 11, and 12) will be judged based on accuracy for words taught in one active condition versus those taught in the other (e.g., retrieval practice with versus without feedback).

Feedback. Participants ($n = 8$) in Contrasts A (feedback vs. no feedback with massed trials) and B (feedback vs. no feedback with spaced trials) address the effect of feedback (see Figure 1). Table 2 displays how we will compare conditions within Contrasts A and B to evaluate both effectiveness and efficiency research questions. For all of these analyses, we use expressive labeling as the primary dependent variable. Therefore, performance for expressive labeling determines when phases change. Phonological precision, receptive performance, and knowledge of semantic content (i.e., location) are secondary variables that will be considered when interpreting the overall results. For example, one condition may exhibit greater accuracy for the primary dependent variable, but not for one or more of the secondary variables.

Figure 1
Study Contrasts

	Feedback	No feedback	Contrasts to Determine Effect of Feedback (RQs 1-6)
Massed	Feedback with massed trials	No feedback with massed trials	Contrast A: Feedback vs. no feedback (massed trials)
Spaced	Feedback with spaced trials	No feedback with spaced trials	Contrast B: Feedback vs. no feedback (spaced trials)

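### No masking to condition is described for outcome coders or visual analysts, which leaves the active-versus-active efficiency questions open to expectation bias that a cheap masking step would reduce.

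*Combined protocol and SAP*

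**What the plan says.** The combined protocol and SAP contains two masking statements, both in section 5.0. Under Dependent Variable Probe: "The primary coder is blind to which sessions are coded for reliability". Under Procedural Fidelity: "The examiner is blind to which sessions are coded for PF". Both concern which sessions are sampled for quality checks.

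The probes "test the 12 target words in sets by condition". For scoring, "Primary and secondary coders double enter data into an electronic form using direct systematic observation of the video recordings". Of comparison-phase sessions the plan says: "They begin with a listening check, then the dependent variable probe, and then the two retrieval practice intervention conditions".

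Section 8.0 states that "Visual analysis is the primary analysis method for single case research design" and that "we consider five features of the data pattern: level, trend, variability, overlap, and consistency". It does not say who makes the judgement or whether condition labels are visible to them. Section 2.0 predicts that feedback will be more efficient than no feedback, and spaced trials more efficient than massed trials.

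The stated safeguards are coder training to .85 point-by-point agreement, double data entry, interobserver agreement on at least 25% of sessions per condition and participant, retraining if agreement falls below .85 for two sessions, and NAP as a supplementary statistic.

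**The concern.** The primary outcome is a listener's judgement of whether a child who is deaf or hard of hearing has produced a short novel word. Section 5.0 itself anticipates self-corrections and articulatory errors. The primary analysis is then a second judgement, made on the graph. If the people making either judgement can tell which word set is under the favoured condition, their expectation can enter at both stages.

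The efficiency questions are the most exposed. RQs 5 and 11 rest on separation of two taught paths plus sessions to mastery. RQs 6 and 12 rest on separation in maintenance plus sessions until performance falls below mastery. Lenient scoring in the expected condition would push the path and the session count the same way. The same scores also decide when phases change.

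**Working it through.** The documents give no power, alpha or sample-size figure bearing on this point, so there is nothing to reproduce. The check sets the provisions side by side and adds one piece of arithmetic.

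1. **What is masked.** The coder is masked to reliability sampling and the examiner to fidelity sampling. No provision in section 5.0 or 8.0 masks a coder or a visual analyst to condition.

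2. **How a coder could learn the condition.** Probe items are grouped by condition. In the comparison phase the probe is followed by both teaching conditions, and feedback is audible in the teaching (section 5.0, Table 1). A coder given the whole recording could work out the key. Baseline and maintenance sessions have no teaching described, so this route does not operate directly on maintenance recordings. For RQs 6 and 12 the exposure comes from a coder who has already scored that child's comparison sessions.

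3. **What the safeguards detect.**
   - Training, double entry and interobserver agreement detect disagreement or entry error. Two coders with the same expectation can agree fully.
   - NAP is calculated by rule, so it is a check on the analyst's eye. It takes the coded scores as input, so it is no check on the coding.

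4. **How coarse the score is.** Inputs from section 5.0: four target words per condition and a 75% criterion for three consecutive sessions. Assumption, not stated: one expressive trial per word per probe.
   - Step per response: 100 / 4 = 25 points.
   - Criterion in words: 0.75 × 4 = 3 of 4.
   - One response rescored from wrong to right takes a set from 2 of 4 (50%) to 3 of 4 (75%), which is the criterion for that session. Mastery needs this in three sessions running, so one rescored response creates mastery only if the other two sessions already qualify.

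5. **Where it matters.** RQs 1–4 and 7–10 compare taught words with untaught novel words, for which section 8.0 expects no increase. Occasional leniency is unlikely by itself to create a large separation there. RQs 5, 6, 11 and 12 compare two taught sets, where a gap of one word in a few sessions can affect the reading.

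**The case against.** **Silence is not evidence of unmasked coding.** A reader might infer that coders and analysts know the key. The documents do not say so. They refer to a coding manual and a procedural manual that are not included, and do not say whether coders receive whole recordings. This stands: the supportable statement is that masking to condition is not described.

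**NAP is a planned check.** It covers comparisons analogous to the visual ones. This stands for the analyst's reading, but not for the coding.

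**The .85 threshold might be read as the expected scoring error.** It is a floor for training and retraining. Its denominator is not specified, and disagreement has no direction, so it does not measure bias.

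**The effect may be small.** Take two conditions with equal, constant true accuracy *p*, independent responses, four trials each, and a rate *e* at which wrong answers are scored correct in one condition only. These are assumptions, not document figures.
- Expected NAP = P(X > Y) + 0.5 × P(X = Y). At *e* = 0.15 it is 0.598 for *p* = 0.4 and 0.554 for *p* = 0.7, against 0.500 without leniency. Both are inside the plan's weak band (0 to .65).
- Sessions to mastery move more. Apparent accuracy is *p* + (1 − *p*)*e*, *q* is the probability of at least 3 of 4 correct, and the mean wait is (1 − *q*³) / ((1 − *q*)*q*³). At *p* = 0.6, *q* goes from 0.475 (*e* = 0) to 0.581 (*e* = 0.15), and the mean wait from 15.9 to 9.8 sessions. At *e* = 0.05 it is 13.3. At *p* = 0.7 it goes from 7.5 (*e* = 0) to 5.8 (*e* = 0.15).

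So leniency alone need not produce a notable NAP, but it could shift a session count that enters the efficiency decision. The actual leniency rate is unknown, and the conclusion does not rest on these values.

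**Conclusion.** The point holds as a gap in the described method. The plan describes no masking to condition for the people who score the primary outcome or judge the graphs, and its remaining safeguards would not reveal a shared expectation in the coding. The size that can be stated is limited: with one trial per word (assumed), one rescored response is worth 25 points in a session, against a 75% criterion required three times in a row. The documents do not allow an estimate of actual bias.

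Two further readings go too far. One is that the whole primary analysis is compromised. The risk lies mainly in RQs 5, 6, 11 and 12, because the other eight questions compare taught with untaught novel words. The other is that relabelling would remove the bias. Relabelled graphs do nothing for coders, the examiner cannot be masked, and a flat control path identifies itself. The change is worth making because it is a better method at low cost.

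**What to change.** **Section 5.0.** State that coders score probe-only clips, cut before teaching begins and labelled with participant, word-set number and a scrambled session code. A team member who does not code that child holds the set-to-condition key and applies the mastery and phase-change rules to the scores. The examiner, who cannot be masked, could do this. State also how word sets are assigned to conditions, which the plan leaves open: if a set always goes with the same condition, the words themselves give the key away.

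**Section 8.0.** State that the final functional-relation decision for the active-versus-active comparisons is made on graphs with condition labels shuffled per child, and is recorded before the key is opened. Report interobserver agreement separately for taught words, since untaught words that stay near zero are easy to agree on.

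**Cost.** Video trimming, relabelling of graphs and about a paragraph of text, using existing team members. Clips must be scored promptly, because scores drive phase changes at three sessions a week. Whoever follows the accruing data to judge baseline stability or an early end to maintenance should not be the masked final rater for that child.

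**What remains.** The flat control path, and teaching that continues in only one set after the other is mastered, can still give hints.
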